## 13. APPENDICES

### APPENDIX A. SCHEDULE OF EVENTS OF SAFETY RUN-IN FOR Q3W DOSING (STUDY PART 1)

Activity	Screening	Cycles 1 and 3					Cycle 2			Cycles $\geq 4$	EOT j	30-day Follow-up f, n
	$\leq 28$ days prior to 1 st dose	Day 1 k	Day 2	Day 3	Day 8 $\pm 1$ day	Day 15 $\pm 1$ day	Day 1 k	Day 8 $\pm 1$ day	Day 15 $\pm 1$ day	Day 1 k		(30-42 Days)
Informed Consent	•											
Demography	•											
Confirm disease diagnosis, stage at diagnosis and current stage	•											
Medical History	•											
Review and Document Inclusion/Exclusion Criteria	•											
Confirm patient continues to satisfy I/E Criteria		C1 only										
Physical examination a	•	•					•			•	•	•
Vital Signs b	•	•			•	•	•	•	•	•	•	•
Weight	•	•				•				•	•	•
Height	•											
B-symptoms	•	•					•			•	•	•
ECOG performance status	•	•					•			•	•	•
Pregnancy test (urine or serum)	•	•					•			•	•	•
Hematology and Chemistry c	•	•	•	•	•	•	•	•	•	•	•	•

Activity	Screening	Cycles 1 and 3					Cycle 2			Cycles $\geq 4$	EOT j	30-day Follow-up f, n
	$\leq 28$ days prior to 1 st dose	Day 1 k	Day 2	Day 3	Day 8 $\pm 1$ day	Day 15 $\pm 1$ day	Day 1 k	Day 8 $\pm 1$ day	Day 15 $\pm 1$ day	Day 1 k		(30-42 Days)
Coagulation c	•	•					•			•	•	•
Urinalysis c	•	•					•			•	•	•
Viral Serology (HBsAg)	•											
Radiologic tumor assessments d	•		Every 6 weeks ( $\pm 1$ week) from Cycle 1 Day 1 (no schedule shift due to dose delays) e delays) e						• f		• f	
Biopsy tumor tissue g	•											
Bone Marrow Assessment h	•		Every 6 weeks ( $\pm 1$ week) from Cycle 1, Day 1 as Clinically Indicated									
ECG (12-lead) i	•	•	•					On Day 1 of Cycles 2 and 4 to coincide with PK draws ( $\pm 1$ hour)			•	•
Pharmacokinetic and Immunogenicity Assessments		See Appendix D										
AE and SAE evaluation 	•	•	•	•	•	•	•	•	•	•	•	•
Concomitant Medication m	•	•	•	•	•	•	•	•	•	•	•	•
Debio 1562 Infusion		•					•			•		
Rituximab Infusion		•					•			•		

- a) Directed physical examination is acceptable while on study treatment and at the 30-day safety Follow-up Visit. Complete examination is required at screening and EOT. Physical examinations may be performed up to 3 days prior to study drug administration on Day 1 of all Cycles.
- b) **Debio 1562** - vital signs (blood pressure, heart rate, temperature, and respiratory rate) will be measured immediately before each administration, every 30 min  $\pm 5$  min during the infusion (if applicable), and immediately after infusion. **Rituximab** - vital signs will be measured immediately before each administration, every 60 min  $\pm 5$  min during the infusion and immediately after infusion. For all cycles, patients must remain in the clinic for safety observation for one hour following completion of their rituximab infusion.
- c) Laboratory assessments may be performed up to 3 days prior to study drug administration in all cycles. All draws on Day 1 of treatment should be pre-dose. In the event of severe toxicity, repeat laboratory tests should be performed within 48 hours, and then followed at least twice weekly until re-treatment criteria are met.  
**Serum Chemistry**- ALB, ALK-P, ALT, AST, BUN, Ca, Cl, Creatinine, Glucose, LDH, Magnesium, Phosphorus, K, Na, Total bilirubin, Total protein, Uric acid, Immunoglobulin levels (IgG, IgA, IgM ).

**Hematology**- Hct, Hgb, Platelet count, RBC count, WBC count with differential.

**Urinalysis** - Appearance, specific gravity and pH, Semi-quantitative dipstick evaluation of glucose, protein, bilirubin, ketones, leukocytes and blood, Microscopic examination of sediment to be performed if urinalysis is positive for WBC, proteins or blood.

**Coagulation tests:** T/INR and aPTT

- d) Radiographic tumor evaluation by CT or PET-CT scan of chest, neck, abdomen and pelvis will be performed within 28 days prior to first dose of study treatment. The anatomical regions to be assessed radiographically post baseline will be determined by individual patients' extent of disease. Whenever possible, the same radiographic scan assessment used at screening (e.g., PET-CT) should be used at all subsequent radiographic evaluations.
- e) Post-baseline disease assessments will be performed every 6 weeks from Cycle 1, Day 1 and will not shift due to dose delays. For patients who are exceptionally granted continued study treatment after completion of 6 cycles, repeat radiographic tumor response assessments can be performed as per local institutional care practice. Ideally, repeat assessments should continue at 6-week ( $\pm$  1 week) intervals and should not be longer than 12-weeks ( $\pm$  4 weeks). Periodic tumor assessment will be conducted using the same imaging modality of prior cycles of treatment until PD, start of any new anti-cancer therapy, or death.
- f) Patients discontinuing Debio 1562 for reasons other than PD will have subsequent clinic visits for radiographic assessment every 12 weeks ( $\pm$  4 weeks) from the time of their last on-study tumor assessment until PD or starting a subsequent anti-cancer therapy. For patients who discontinue for PD, no radiographic scans will be required at the EOT visit or the follow-up visits. All patients will be followed for survival every 12 weeks ( $\pm$  4 weeks) from the time of the 30-day safety Follow-up visit, for up to one year from the last patient's first dose (Cycle 1 Day 1). Patients will not be required to visit the clinic for survival follow-up.
- g) Patients must have available a pathology-informed tumor biopsy sample representative of the current disease, [REDACTED].
- h) If applicable, a bone marrow biopsy or aspirate will be performed within 3 months prior to first dose. A repeat bone marrow biopsy or aspirate will be required for patients with bone marrow infiltration at baseline who have a CR by imaging and physical examination, and will, in case possible and deemed acceptable by the Investigator, be performed every 6 weeks as clinically indicated. In order to better understand the effect of Debio 1562 on WBCs, bone marrow biopsies/aspirates may also be requested for those patients who experience grade 4 cytopenias.
- i) The screening ECG will be performed within 14 days prior to first treatment. In Cycles 1 and 3, ECGs will be performed within three hours prior to dose, at the end of the Debio 1562 infusion (to coincide with Cmax and PK blood draw) and  $24 \pm 4$  hours after infusion. An ECG will be performed on Day 1 of Cycles 2 and 4 (inclusive) to coincide with the pre-dose PK blood draw. An ECG at the 30-day Follow-up visit is not required unless clinically indicated or if the EOT assessment was missed.
- j) EOT visit should occur within 7 days of the decision to discontinue study treatment.
- k) Cycle 1 Day 1 assessments (ECOG, weight, B Symptoms and pregnancy test) do not need to be repeated if they are collected within 3 days of study drug administration. For all other cycles, the Day 1 window is  $\pm 3$  days.
- l) The period of safety observation extends from the time of consent until 30 days after the patient's last study treatment or until the AEs has resolved or stabilized or an outcome has been reached, whichever comes first.
- m) Concomitant medications should be collected beginning from 4 weeks prior to Cycle 1, Day 1 until the end of the period of safety observation.
- n) In the event that a patient is unable to return to the clinic for a follow-up visit, telephone contact with the patient to assess AEs, concomitant medications, anti-cancer treatments will be conducted.

## APPENDIX B. SCHEDULE OF EVENTS OF COHORT A FOR Q3W DOSING (STUDY PART 2 AND 3)

Activity	Screening	Cycles 1 and 2					Cycles 3-6 q	EOT 	30-day Follow-up g, p
		Day 1 m	Day 2	Day 3	Day 8 ±1 day	Day 15 ±1 day			
	≤28 days prior to 1 st dose								(30-42 Days)
Informed Consent	•								
Demography	•								
Confirm disease diagnosis, stage at diagnosis and current stage	•								
Medical History	•								
Review and Document Inclusion/Exclusion Criteria	•								
Confirm patient continues to satisfy I/E Criteria		C1 only							
Physical examination a	•	•					•	•	•
Vital Signs b	•	•			•	•	•	•	•
Health-related Quality of Life c		•					•	•	•
Weight	•	•					•	•	•
Height	•								
B-symptoms	•	•					•	•	•
ECOG performance status	•	•					•	•	•
Pregnancy test (urine or serum)	•	•					•	•	•
Hematology and Chemistry d	•	•	•	•	•	•	•	•	•

Activity	Screening	Cycles 1 and 2					Cycles 3-6 q	EOT 	30-day Follow-up g, p
	≤28 days prior to 1st dose	Day 1 m	Day 2	Day 3	Day 8 ±1 day	Day 15 ±1 day	Day 1 m		(30-42 Days)
Coagulation 	•	•					•	•	•
Urinalysis d	•	•					•	•	•
Viral Serology (HBsAg)	•								
Radiologic tumor Assessments e	•		Every 6 weeks (± 1 week) from Cycle 1, Day 1 (no schedule shift due to dose delays) f					• g	• g
Biopsy tumor tissue h	•								
Bone Marrow Assessment i	•		Every 6 weeks (± 1 week) from Cycle 1, Day 1 as Clinically Indicated						
ECG (12-lead) k	•	•	•				•	•	•
Pharmacokinetic and Immunogenicity Assessments		See Appendix E							
AE and SAE evaluation n	•	•	•	•	•	•	•	•	•
Concomitant Medication o	•	•	•	•	•	•	•	•	•
Debio 1562 Infusion		•					•		
Rituximab Infusion		•					•		

- a) Directed physical examination is acceptable while on study treatment and at the 30-day safety Follow-up Visit. Complete examination is required at screening and EOT. Physical examinations may be performed up to 3 days prior to study drug administration on Day 1 of all Cycles.
- b) **Debio 1562** - vital signs (blood pressure, heart rate, temperature, and respiratory rate) will be measured immediately before each administration, every 30 min ± 5 min during the infusion (if applicable), and immediately after infusion. **Rituximab** - vital signs will be measured immediately before each administration, every 60 min ± 5 min during the infusion and immediately after infusion. Patients will remain in the clinic under monitoring for four hours after completion of the rituximab infusion for the first cycle. Post-administration safety monitoring could potentially be shortened (i.e. < 4 hours but at least 1 hour) following subsequent administration of rituximab, based on the judgement of the investigator. Patients receiving Debio 1562 only will also remain in the clinic under monitoring for one hour.
- c) HRQoL assessment at Day 1 of each cycle will be performed prior to Debio 1562 infusion. In patients who exceptionally continue the study treatment beyond C6, the last HRQoL assessment will be performed at C7D1 before the infusion and no additional HRQoL assessment will be completed at 30-day follow up

visit.

d) Laboratory assessments may be performed up to 3 days prior to study **drug administration in all cycles**. If the screening laboratory assessments are performed within 3 days prior drug administration on Day 1 of Cycle 1, no assessments need to be repeated on Day 1 of Cycle 1. All draws on days of treatment should be pre-dose. In the event of severe toxicity, repeat laboratory tests should be performed within 48 hours, and then followed at least twice weekly until retreatment criteria are met.

**Serum Chemistry**- ALB, ALK-P, ALT, AST, BUN, Ca, Cl, Creatinine, Glucose, LDH, Magnesium, Phosphorus, K, Na, Total bilirubin, Total protein, Uric acid, Immunoglobulin levels (IgG, IgA, IgM ).

**Hematology**- Hct, Hgb, Platelet count, RBC count, WBC count with differential.

**Urinalysis** - Appearance, specific gravity and pH, Semi-quantitative dipstick evaluation of glucose, protein, bilirubin, ketones, leukocytes and blood, Microscopic examination of sediment to be performed if urinalysis is positive for WBC, proteins or blood.

**Coagulation tests**: T/INR and aPTT.

If deemed necessary by the Investigator an additional hematological assessment can be performed on Day 15 of Cycles 3-6.

e) Radiographic tumor evaluation by CT or PET-CT scan of chest, neck, abdomen and pelvis will be performed within 28 days prior to first dose of study treatment. The anatomical regions to be assessed radiographically post baseline will be determined by individual patients' extent of disease. Whenever possible, the same radiographic scan assessment used at screening (e.g., PET-CT) should be used at all subsequent radiographic evaluations.

f) Post-baseline disease assessments will be performed every 6 weeks from Cycle 1, Day 1 and will not shift due to dose delays. For patients who are exceptionally granted continued study treatment after completion of 6 cycles, repeat radiographic tumor response assessments can be performed as per local institutional care practice. Ideally, repeat assessments should continue at 6-week ( $\pm$  1 week) intervals and should not be longer than 12-weeks ( $\pm$  4 weeks). Periodic tumor assessment will be conducted using the same imaging modality of prior cycles of treatment until PD, start of any new anti-cancer therapy, or death.

g) Patients discontinuing Debio 1562 for reasons other than PD will have subsequent clinic visits for radiographic assessment every 12 weeks ( $\pm$  4 weeks) from the time of their last on-study tumor assessment until PD or starting a subsequent anti-cancer therapy. For patients who discontinue for PD, no radiographic scans will be required at the EOT visit or the follow-up visits. All patients will be followed for survival every 12 weeks ( $\pm$  4 weeks) from the time of the 30-day safety Follow-up visit, for up to one year from the last patient's first dose (Cycle 1 Day 1). Patients will not be required to visit the clinic for survival follow-up.

h) Patients must have available a pathology-informed tumor biopsy sample representative of the current disease, [REDACTED].

i) If applicable, a bone marrow biopsy or aspirate will be performed within 3 months prior to first dose. A repeat bone marrow biopsy or aspirate will be required for patients with bone marrow infiltration at baseline who have a CR by imaging and physical examination, and will, in case possible and deemed acceptable by the Investigator, be performed every 6 weeks as clinically indicated. In order to better understand the effect of Debio 1562 on WBCs, bone marrow biopsies/aspirates may also be requested for those patients who experience grade 4 cytopenias.

[REDACTED]

[REDACTED]

k) The screening ECG will be performed within 14 days prior to first treatment. In Cycles 1 and 2, ECGs will be performed within three hours prior to dose, at the end of the Debio 1562 infusion (to coincide with Cmax and PK blood draw) and  $24 \pm 4$  hours after infusion. An ECG will be performed on Day 1 of Cycles 3-6 to coincide with the pre-dose PK blood draw. An ECG at the 30-day Follow-up visit is not required unless clinically indicated or if the EOT assessment was missed.

l) EOT visit should occur within 7 days of the decision to discontinue study treatment.

m) Cycle 1 Day 1 assessments (ECOG, weight, B Symptoms and pregnancy test) do not need to be repeated if they are collected within 3 days of study drug administration. For all other cycles, the Day 1 window is  $\pm 3$  days.

n) The period of safety observation extends from the time of consent until 30 days after the patient's last study treatment or until the AEs has resolved or stabilized or an outcome has been reached, whichever comes first.

- o) Concomitant medications should be collected beginning from 4 weeks prior to Cycle 1, Day 1 until the end of the period of safety observation.
- p) In the event that a patient is unable to return to the clinic for a follow-up visit, telephone contact with the patient to assess AEs, concomitant medications, and anti-cancer treatments will be conducted.
- q) Permission to prolong the study treatment could be exceptionally granted by Study Sponsor if patients are deriving benefit from the study treatment and after complete presentation of the individual case by the Study Investigator, particularly the medical justification for extending the treatment and the re-assessment of the risk/benefit balance. The Sponsor's decision will consider the availability of IMP at the time of request. A report of the discussions with the Sponsor must be filed in the source documentation.

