**APPENDIX C. SCHEDULE OF EVENTS OF COHORT B FOR QW DOSING (STUDY PART 2 AND 3)**

Activity	Screening	Cycles 1 and 2					Cycles 3-6 q			EOT 	30-day Follow-up g, p
		≤28 days prior to 1 st dose	Day 1 m	Day 2	Day 3	Day 8 (-1 to +3 days)	Day 15 (-1 to +3 days)	Day 1 m	Day 8 (-1 to +3 days)	Day 15 (-1 to +3 days)	
Informed Consent	•										
Demography	•										
Confirm disease diagnosis, stage at diagnosis and current stage	•										
Medical History	•										
Review and Document Inclusion/Exclusion Criteria	•										
Confirm patient continues to satisfy I/E Criteria		C1 only									
Physical examination a	•	•			•	•	•	•	•	•	•
Vital Signs b	•	•			•	•	•	•	•	•	•
Health-related Quality of Life c		•					•			•	•
Weight	•	•			•	•	•	•	•	•	•
Height	•										
B-symptoms	•	•			•	•	•	•	•	•	•
ECOG performance status	•	•			•	•	•	•	•	•	•
Pregnancy test (urine or serum)	•	•					•			•	•
Hematology and Chemistry d	•	•	•	•	•	•	•	•	•	•	•

Activity	Screening	Cycles 1 and 2					Cycles 3-6 a			EOT 	30-day Follow-up b, p
	≤28 days prior to 1st dose	Day 1 m	Day 2	Day 3	Day 8 (-1 to +3 days)	Day 15 (-1 to +3 days)	Day 1 m	Day 8 (-1 to +3 days)	Day 15 (-1 to +3 days)		(30-42 Days)
Coagulation d	•	•			•	•	•	•	•	•	•
Urinalysis d	•	•			•	•	•	•	•	•	•
Viral Serology (HBsAg)	•										
Radiologic tumor assessments e	•		Every 6 weeks ( $\pm$ 1 week) from Cycle 1, Day 1 (no schedule shift due to dose delays) f						• g	• g	
Biopsy tumor tissue h	•										
Bone Marrow Assessment i	•		Every 6 weeks ( $\pm$ 1 week) from Cycle 1, Day 1 as Clinically Indicated								
ECG (12-lead) k	•	•	•		•	•	•	•	•	•	•
Pharmacokinetic and Immunogenicity Assessments		See Appendix F									
AE and SAE evaluation n	•	•	•	•	•	•	•	•	•	•	•
Concomitant Medication o	•	•	•	•	•	•	•	•	•	•	•
Debio 1562 Infusion		•			•	•	•	•	•		
Rituximab Infusion		•					•				

a) Directed physical examination is acceptable while on study treatment and at the 30-day safety Follow-up Visit. Complete examination is required at screening and EOT. Physical examinations may be performed up to 3 days prior to study drug administration on Day 1 of all Cycles.

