10.3 Safety Analyses

All safety analyses will be conducted on the safety population. All summaries will present data by cohort, unless otherwise specified. Safety evaluations will be based on the incidence and severity of adverse events (AEs), clinically significant changes or abnormalities in the subject's laboratory results, vital signs, physical examination, ECG, and Eastern Cooperative Oncology Group (ECOG) score.

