10.3.3 Clinical Laboratory Evaluations

Screening laboratory evaluations (hematology, clinical chemistry, urinalysis, and coagulation) may be performed within 28 days before the first dose. Repeat testing will be performed as outlined in schedule of events ([Appendix A](#), [Appendix B](#) and [Appendix C](#)) and as clinically indicated. Clinical laboratory results will be classified as Low, Normal, and High, or Normal/Abnormal according to the lab normal ranges, and will be graded according to NCI CTCAE, Version 4.03.

All hematology, serum chemistry, urinalysis, and coagulation will be listed per subject for each assessment and descriptive statistics will be tabulated for selected criteria detailed below by cohort and overall. SI units will be used for listing and reporting. Changes and percent changes from baseline in hematology and serum chemistry will be calculated for each subject and subsequently summarized by cohort and overall. Shifts from baseline in hematology and serum chemistry values will also be summarized by CTCAE grade within cohorts and overall. Only scheduled visits will be included in change from baseline summary tables; however, unscheduled visits will be included in worse post-baseline shift tables, liver function tests summaries, and listings.

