10.3.3.1 Hematology

Hematology will include: hematocrit (HCT), hemoglobin (HGB), platelet count (PLAT), red blood cell (RBC) count, white blood cell (WBC) count with differential [i.e. neutrophils count (NEUT), lymphocyte (LYM), monocytes (MONO), eosinophils, and basophils (BASO)].

Shift from baseline to worst post-baseline low and high CTCAE grade for hematology parameters will be presented in a table for: HGB, RBC, NEUT, PLAT, LYM and WBC. In the

shift table based on being lower than a lower normal limit (worst low), a value above the upper normal limit will be considered as grade 0.

10.3.3.2 *Serum chemistry*

Serum chemistry will include: albumin (ALB), alkaline phosphatase (ALP), alanine aminotransferase (ALT), aspartate aminotransferase (AST), blood urea nitrogen (UREAN), calcium (CA), chloride (CL), creatinine (CREAT), glucose (GLUC), lactate dehydrogenase (LDH), magnesium (MG), phosphorus (PHOS), potassium (K), Sodium, total bilirubin (BILI), total protein (PROT), Uric acid (URATE), and Immunoglobulin levels (i.e., IgG, IgA, and IgM).

Shift from baseline to worst post-baseline CTCAE grade for serum chemistry parameters (i.e. ALB [worst low only], ALP, ALT, AST, CREAT, BILI, and URATE [worst high only], and PHOS, CA, CL, GLUC, MG, K, and SODIUM [both worst low and worst high]) will be presented in separate tables for CTCAE based on being higher or lower than normal limits, where applicable. In the shift table based on being higher than an upper normal limit (worst high) a value below the lower normal limit will be considered as grade 0. Likewise, in the shift table based on being lower than a lower normal limit (worst low), a value above the upper normal limit will be considered as grade 0.

10.3.3.3 *Urinalysis and Pregnancy Test*

Urinalysis includes: appearance, specific gravity, and pH. Microscopic examination of sediment is to be performed if the specimen is positive for WBCs, proteins, or blood. Semi quantitative evaluations include using dipsticks for glucose, protein, bilirubin, ketones, leukocytes and blood. Urinalysis and pregnancy test laboratory results will be presented in separate listings.

Coagulation

Coagulation tests include: prothrombin time, International Normalized Ratio (INR), and activated partial thromboplastin time (aPTT). Coagulation results will be presented in a data listing.

10.3.3.4 *Liver Function Test*

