Clinically significant values in liver function tests will be summarized by the following categories using the maximum value while on treatment. The denominator for the summaries will be the number of subjects who had at least one non-missing value during treatment. Please note that the categories for each test are not mutually exclusive:

- AST:
 - o > 1xULN & ≤ 3xULN;
 - o > 3xULN & ≤ 5xULN;
 - o > 5xULN & ≤ 10xULN;
 - o > 10xULN & ≤ 20xULN;

- o > 20xULN;
- ALT:
 - o > 1xULN & ≤ 3xULN;
 - o > 3xULN & ≤ 5xULN;
 - o > 5xULN & ≤ 10xULN;
 - o > 10xULN & ≤ 20xULN;
 - o > 20xULN;
- AST or ALT:
 - o > 1xULN & ≤ 3xULN;
 - o > 3xULN & ≤ 5xULN;
 - o > 5xULN & ≤ 10xULN;
 - o > 10xULN & ≤ 20xULN;
 - o > 20xULN;
- Total bilirubin (TBL):
 - o > 1xULN & ≤ 2xULN;
 - o > 2xULN;
- Alkaline Phosphatase:
 - o > 1.5xULN;
- (AST or ALT) and TBL (all tests must be conducted within 72 hours):
 - o AST or ALT > 3xULN and TBL > 1.5xULN & ≤ 2xULN;
 - o AST or ALT > 3xULN and TBL > 2xULN;
- (AST or ALT) and ALP and TBL (all tests must be conducted within 72 hours):
 - o AST or ALT > 3xULN and ALP < 2xULN and TBL > 2xULN.

10.3.3.5 *Vital Signs*

Vital sign measurements will include blood pressure, heart rate, temperature, and respiratory rate. Height will only be measured at screening and weight will be measured as indicated in the schedule of events ([Appendix A](#), [Appendix B](#) and [Appendix C](#)). A change and percent change from baseline summary table, and a listing of measurement values by visit, will be provided for vital signs. Only scheduled visits will be included in change from baseline summary tables. All visits will be included in listings.

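### From Cycle 3 cohort B has three times cohort A's scheduled laboratory draws, so by-cohort worst-grade and maximum-liver tables can show more toxicity with QW at equal true risk

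*Protocol*

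**What the plan says.** **Schedule.** Protocol Appendices B and C (repeated in SAP Appendices B and C) have the same hematology and chemistry days in Cycles 1-2: Days 1, 2, 3, 8 and 15. In Cycles 3-6 cohort A has Day 1 only, and cohort B has Days 1, 8 and 15. Footnote d of Appendix B adds for cohort A: "If deemed necessary by the Investigator an additional hematological assessment can be performed on Day 15 of Cycles 3-6". It adds no chemistry. Both appendices also say: "In the event of severe toxicity, repeat laboratory tests should be performed within 48 hours".

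**Tables.** SAP 10.3 states: "All summaries will present data by cohort, unless otherwise specified". SAP 10.3.3.1 adds: "Shift from baseline to worst post-baseline low and high CTCAE grade for hematology parameters will be presented in a table"; SAP 10.3.3.2 does the same for chemistry. Under SAP 10.3.3.4, liver tests are "summarized by the following categories using the maximum value while on treatment". SAP 10.3.3 specifies that "unscheduled visits will be included in worse post-baseline shift tables, liver function tests summaries, and listings". The change-from-baseline tables use scheduled visits only. The laboratory text contains no worst-grade or maximum-value table limited to draws that both cohorts share, and no count of assessments per patient.

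**The concern.** A worst grade or a maximum taken over more draws can only stay the same or rise. An abnormality that starts mid-cycle after Cycle 2 and recovers before the next Day 1 can be recorded in cohort B and missed in cohort A. Two kinds of abnormality create no gap: one that lasts to the next Day 1, and one that the same patient already showed at that grade in Cycles 1-2.

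Laboratory change is part of a primary endpoint (Protocol 2.2.1). Limiting neutropenia is a stated reason for the weekly regimen (Protocol 1.6), and neutropenia and hepatic damage are named monitoring priorities (Protocol 10.6.3). Patients are randomized 1:1 while both cohorts are open, so readers will compare the two columns. Unequal ascertainment would tilt that reading against QW.

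**Working it through.** **Counts, from Protocol Appendices B and C.**
- Cycles 3-6: A = 1 × 4 = 4; B = 3 × 4 = 12. With every optional count, A hematology = 8 and A chemistry stays at 4.
- Post-baseline over six cycles, with end of treatment (EOT) and 30-day follow-up: A = 4 + 5 + 4 + 2 = 15; B = 4 + 5 + 12 + 2 = 23.
- A cohort B patient who switches to Q3W after cycle k follows the cohort A schedule (Protocol 5.7.4.1) and has 3(k − 2) + (6 − k) draws in Cycles 3-6. That is 4, 6, 8 or 10 for k = 2, 3, 4 or 5.

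The plan states no figure on this point, so there is none to reproduce.

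**Size, by assumption.** The documents give no episode risk, duration or onset. I assume:
- at most one episode per 21-day cycle, with risk q of 5-20%, equal in both cohorts, lasting d days;
- six completed cycles, nominal days, no switch and no unscheduled tests;
- an episode is recorded if a scheduled draw falls inside it.

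Draw days are {2, 3, 8, 15, 22} in Cycles 1-2 for both cohorts. In Cycles 3-6 they are {22} for A, {15, 22} for A with optional counts, and {8, 15, 22} for B. Day 22 is the next Day 1, with EOT standing in after Cycle 6. Call the detection probabilities p12 and p36.

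- Independent risk each cycle: P = 1 − (1 − q·p12)² (1 − q·p36)⁴.
- Same patients every cycle: P = q[1 − (1 − p12)² (1 − p36)⁴].

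Example with uniform onset, d = 4, q = 10%, independent risk: p12 = 14/21; p36 = 4/21 (A), 8/21 (A with optional counts), 12/21 (B).
- A: 1 − 0.9333² × 0.9810⁴ = 19.3%.
- B: 1 − 0.9333² × 0.9429⁴ = 31.2%.
- Gap 11.8 points. With optional counts A is 25.4% and the gap is 5.7.

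Gap B − A in percentage points, without optional counts, at q = 5 / 10 / 20%:

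| Episode length | Independent risk, uniform onset | Independent risk, onset Days 5-12 | Same patients, either onset |
|---|---|---|---|
| 4 days | 6.7 / 11.8 / 18.1 | 10.3 / 18.6 / 30.2 | 0.2 to 3.55 |
| 7 days | 10.9 / 17.6 / 22.4 | 16.7 / 27.9 / 37.8 | 0 |
| 10 days | 8.4 / 13.5 / 16.7 | 16.7 / 27.9 / 37.8 | 0 |
| 14 days | 5.3 / 8.3 / 9.9 | 6.9 / 10.9 / 13.2 | 0 |
| 17 days | 3.0 / 4.6 / 5.4 | 0 | 0 |
| 21 days | 0 | 0 | 0 |

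- Largest uniform-onset value: d = 7, q = 20%, p36 = 1/3 in A and 1 in B. Then 0.64 × 0.9333⁴ − 0.8⁶ = 0.4857 − 0.2621, or 22.4 points.
- Largest value overall: with onset on Days 5-12 and d = 7 or 10, cohort A detects none of its Cycle 3-6 episodes. Then 0.64 − 0.2621, or 37.8 points.
- Largest same-patient value: 0.2 × [(3/7)² − (3/7)⁶] = 0.0355.
- With every optional count (hematology only), the independent-risk maximum is 9.9 points for uniform onset and 21.6 for Days 5-12.
- Between the two extremes, I let patient risk follow a Beta distribution with mean 10%, for 4- or 7-day episodes over both onset patterns. The gap is 4.3-8.1 points at within-patient correlation 0.5 and 0.7-2.9 at 0.9.
- With four cycles completed instead of six, independent risk gives 3.5-23.0 points for 4- or 7-day episodes.

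**The case against.** **The tables are descriptive, and the draws follow the regimen.** SAP 10.2.1 plans no formal comparison between cohorts. Protocol 8.10 requires laboratory review before every Debio 1562 dose, so the extra cohort B draws belong to weekly dosing. This stands: no planned test is wrong, and the point concerns how the tables are read.

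**Other tests narrow the gap.** Laboratory tests are also done when clinically indicated (Protocol 8.10, SAP 10.3.3), so symptoms can prompt one without an earlier abnormal draw, and the result enters the worst-value tables. Optional Day 15 counts, early discontinuation and switches to Q3W also shrink the gap. Protocol 1.9 reports three patients on QW treatment on 14 April 2020. All of this stands. The repeat tests after severe toxicity help less, because the toxicity must first be detected.

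**Detection can change what follows.** Under Protocol 5.9.1, unmet retreatment criteria on Day 8 or 15 in cohort B lead to a skipped dose and G-CSF. Later counts in B may then differ for reasons the model omits, so the net direction for hematology is less certain than the detection argument alone suggests.

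**Other displays exist.** Scheduled-visit change from baseline, subject listings and grouped neutropenia adverse-event tables are planned. None is a matched worst-grade or maximum-value table.

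**Cohort A may not be uniform.** Protocol 10 pools relapsed DLBCL patients recruited before Amendment 3 with cohort A, while SAP 9.1 lists the run-in expansion as separate reporting cohorts. If those patients followed the run-in schedule (Appendix A), which the documents do not state, they have 5 + 3 = 8 draws in Cycles 3-6 and no Day 2 or Day 3 draw in Cycle 2.

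**Stronger readings do not hold.** A reader might infer that three times the draws means three times the recorded toxicity, or a gap near 38 points. The 3:1 ratio covers Cycles 3-6 only; over the whole course it is 23:15, about 1.5:1. The 38 points need the least favorable combination of assumptions. A reader might also infer that the committee's dosing decisions were distorted. The cohort B reviews are triggered after one or two cycles, when draw days match, so they are largely unaffected.

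**Conclusion.** The concern holds as a limited problem of ascertainment in descriptive tables. The counts of 4 versus 12 (8 versus 12 for hematology at most) and 15 versus 23 come straight from the schedules. SAP 10.3.3 uses statistics that depend on how often patients are sampled. The detection effect runs against QW, for short abnormalities first appearing after Cycle 2 in patients who reach Cycle 3.

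Its size is an assumption, not a finding. Under the stated model it is 0 to about 22 points with uniform onset, up to about 38 only with onset confined to Days 5-12 and independent risk each cycle, and below 3.6 if the same patients are affected every cycle. Clinically indicated tests, optional counts, dropout and switching all pull it down. The documents do not support saying that QW will look worse by any particular amount, or that a planned inference is invalid. This is a cheap improvement to consider.

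**What to change.** In SAP 10.3.3:

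1. Keep the all-visit worst-grade and maximum-liver tables. Footnote them with the unequal schedule from Cycle 3, the number of assessments per patient by cohort, and the patients who switched to Q3W.
2. Add one supplementary, not primary, by-cohort set of the same tables. Restrict it to scheduled draws shared by cohorts A and B from first dose through the pre-dose Cycle 3 Day 1 draw: Cycles 1-2 Days 1, 2, 3, 8 and 15, plus Cycle 3 Day 1. That is 4 + 5 + 1 = 10 post-baseline draws in each cohort.
3. Footnote that the Day 8 and Day 15 windows differ (±1 day in A, −1 to +3 days in B). Footnote also that time since last dose differs: about 14 versus 7 days at Day 15, and about 21 versus 7 at the next Day 1. The set matches draw days, not time since dosing.
4. If the pre-Amendment 3 relapsed DLBCL patients are pooled with cohort A, show them separately in this set, or exclude them if they followed the run-in schedule.

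The cost is a few extra tables and footnotes from data already collected, with no change to monitoring. The matched set omits later events, which remain in the all-visit tables.
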